Skin biopsies (optional) ^o		X				X					X		X				
Randomization	X																
Photography ^p	X	X				X					X				X		X
Telephone contact ^p			X		X		X		X								
Study treatment administration ^q		X				X		X		X	X	X	X	X			
Subject diary distribution/collection/review ^r		X				X		X		X	X	X	X	X	X	X	X
AE/SAE review	X										Continuously						
Concomitant medication review	X ^s										Continuously						

Abbreviations: ADA, anti-drug antibody; AE, adverse event; BSA, body surface area; CDLQI, Children's Dermatology Life Quality Index; D, day; DLQI, Dermatology Life Quality Index; ECG, electrocardiogram; EOS, end of study; ET, early termination; FSH, follicle stimulating hormone; IASI, Ichthyosis Area and Severity Index; IGA, Investigator Global Assessment; IgE, immunoglobulin E; iQoL-32, Ichthyosis Quality of Life- 32 items; NASA, Netherton Area and Severity Assessment; NRS, Numeric Rating Scale; PGI-C, Patient Global Impression of Change; PGI-S, Patient Global Impression of Severity; PK, pharmacokinetics; SAE, serious adverse event; SC, subcutaneously; SoA, Schedule of Activities; TB, tuberculosis; TEWL, transepidermal water loss; W, week; WOCBP, woman of childbearing potential.

^a All subjects will receive ANB019 during the open-label extension period starting on Day 113 (Week 16) visit until Day 197 (Week 28) visit. The placebo-controlled period ends on Day 113 (Week 16) visit, before study treatment administration. The open-label extension period starts when the study treatment is administered on Day 113 (Week 16) visit.

Table 1: Schedule of Activities (Continued)

^b The ET visit will include all procedures to be done at the ET/EOS visit (Day 281/Week 40 visit).

^c Adolescent subjects who reach 18 years of age during the study must be reconsented as adults.

^d Height to be measured at screening only for subjects \geq 18 years of age, and at screening, Day 113 (Week 16), and Day 281 (Week 40)/ET for subjects $<$ 18 years of age.

^e Refer to [Section 8.1](#) for details and instructions regarding pain and pruritus NRSs (worst and average), iQoL-32 (subjects \geq 15 years of age only), DLQI (subjects \geq 16 years of age), CDLQI (subjects $<$ 16 years of age), PGI-S, PGI-C, BSA, IGA, IASI, NASA, and TEWL. PGI-C is not to be performed at Day 1.

^f Refer to [Section 8.2.4](#) for details regarding the complete physical examination.

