7.2 SUBJECT DISCONTINUATION/WITHDRAWAL FROM THE STUDY

A subject may withdraw from the study at any time at his or her own request or may be withdrawn at any time at the discretion of the Investigator for safety, behavioral, compliance, or administrative reasons.

In case of early withdrawal from the study treatment and the study, the subject will be required to attend the ET visit (see the SoA in [Section 1.3](#)). After the ET visit, additional follow-up visits may be scheduled to follow any ongoing AE. Subjects must be withdrawn from the study under the following circumstances, any SAE or significant AE which, in the opinion of the Investigator, warrant study discontinuation for safety reasons, or pregnancy occurring through the EOS, which should be followed up until outcome.

The following events are considered sufficient reasons for discontinuing a subject from the study treatment and/or the study:

- Pregnancy (Refer to [Appendix 1](#) and [Section 8.2.1.8](#))
- Significant deviation/lack of compliance with protocol
- Any significant AE, laboratory abnormality, or other medical condition or situation occurs such that continued participation in the study would not be in the best interest of the subject in the opinion of the Investigator
- Disease progression which requires discontinuation of the study treatment
- Withdrawal of consent
- Lost to follow-up
- Use of any prohibited medication or treatment that in the opinion of the Investigator necessitates the subject being withdrawn (Refer to [Section 6.5.2](#))

DocuSign Envelope ID: E4BE9C16-DB1E-4354-B874-2109B7254DAA

Efficacy and Safety of ANB019 in Subjects with Ichthyosis
Protocol ANB019-206

Version 1.0
30 October 2020

- Termination of the subject participation by the Investigator or Sponsor

The reason for subject discontinuation or withdrawal from the study will be recorded on the eCRF.

If a subject withdraws from the study, he or she may request destruction of any samples taken and not tested, and the Investigator must document this in the study center study records.

See SoA (see [Section 1.3](#)) for data to be collected at the time of study discontinuation and follow-up and for any further evaluations that need to be completed.

Subjects withdrawing from the study prematurely for reasons other than a study treatment-related AE may be replaced at the discretion of the Sponsor.

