8.2.1.4 TIME PERIOD AND FREQUENCY FOR EVENT ASSESSMENT AND FOLLOW-UP

The occurrence of an AE or SAE may come to the attention of study personnel during study visits and interviews of a study subject presenting for medical care, or upon review by a study monitor.

All AEs including local and systemic reactions will be captured on the appropriate eCRF. Information to be collected includes event description, date of onset, clinician's assessment of severity, seriousness, relationship to study treatment (assessed only by those with the training and authority to make a diagnosis), action taken, and outcome of the event. All AEs occurring while on study must be documented appropriately regardless of relationship (see [Section 8.2.1.3.2](#)). All AEs will be followed to adequate resolution.

Study site personnel will note the occurrence and nature of each subject's medical condition(s) present prior to the informed consent signature in the appropriate section of the source document and eCRF. During the study, site personnel will note any change in the condition(s) and the occurrence and nature of any AE. Care will be taken not to introduce bias when detecting AEs and/or SAEs. Open-ended and nonleading verbal questioning of the subject is the preferred method to inquire about AE occurrences.

DocuSign Envelope ID: E4BE9C16-DB1E-4354-B874-2109B7254DAA

Efficacy and Safety of ANB019 in Subjects with Ichthyosis
Protocol ANB019-206

Version 1.0
30 October 2020

Should a subject experience an AE at any time after the screening visit informed consent signature until the end of participation in the study, the event will be recorded as an AE in the source document and eCRF. Any SAE related to the study participation (eg, screening procedure) will be recorded in the source document and eCRF from the time consent is given to participate in the study until the end of participation in the study (EOS/ET visit).

Investigators are not obligated to actively seek AEs or SAEs after conclusion of the study participation. However, if the Investigator learns of any SAE, including a death, at any time after a subject has been discharged from the study, and he or she considers the event to be reasonably related to the study treatment or study participation, the Investigator must promptly notify the pharmacovigilance unit.

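### Subjects withdrawn from the study have one required ET visit with no minimum interval after the last dose, so active collection of new AEs can end about one half-life after it

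*Protocol*

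**What the plan says.** Protocol Section 7.2 requires a subject who leaves both treatment and study to attend an ET visit. Table 1, footnote b (Section 1.3) defines what is done there: "The ET visit will include all procedures to be done at the ET/EOS visit (Day 281/Week 40 visit". Neither place says how long after the last dose it must fall. The ±5-day window in the EOS/ET column belongs to Day 281 and sets no interval for an early ET. On later contact, Section 7.2 says only: "After the ET visit, additional follow-up visits may be scheduled to follow any ongoing AE".

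Section 8.2.1.4 sets the collection period. For AEs it runs from the "informed consent signature until the end of participation in the study, the event will be recorded as an AE". The sentence on SAEs related to study participation has the same end and identifies it: "until the end of participation in the study (EOS/ET visit". After that, "Investigators are not obligated to actively seek AEs or SAEs after conclusion of the study participation". Two duties remain. Reported AEs are followed until resolved or stable. And "if the Investigator learns of any SAE, including a death, at any time after a subject has been discharged from the study", and considers it reasonably related to treatment or participation, it must be notified.

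Withdrawal is mandatory in some cases: "Subjects must be withdrawn from the study under the following circumstances, any SAE or significant AE which, in the opinion of the Investigator", warrants it for safety. Another listed reason is "Termination of the subject participation by the Investigator or Sponsor".

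Two groups are outside the point. Subjects who stop treatment but stay in the study complete the remaining procedures (Section 7.1). Those stopped for rescue use are asked to complete follow-up (Section 6.5.3).

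**The concern.** Section 4.4 gives a half-life of about 28 days with persistent pharmacodynamic activity, and doses are 28 days apart. A subject who leaves at a dosing visit, or between two visits, therefore has substantial drug exposure when active collection of new events stops.

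The provisions that continue after the ET visit do not fill this gap. Optional visits and follow-up to resolution concern events already known. The later SAE duty depends on the Investigator hearing of the event and judging it related. New non-serious AEs can go unrecorded, as can SAEs that are not heard of or are judged unrelated. Those exposed to this include subjects withdrawn because an SAE or significant AE warranted it, whose later safety course is of particular interest.

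**Working it through.** **Inputs.** Doses on Days 1, 29, 57, 85, 113, 141, 169 and 197; assessments at dosing visits are made before dosing (Protocol Section 1.3). Windows in Table 1: none at Day 1, ±2 days at Day 29, ±4 at Day 57 and later dosing visits, ±5 at Day 281. Half-life about 28 days (Section 4.4). Stated safety follow-up 8 weeks (Section 4.1). Planned dropout 11%, taking 16 to 14 on ANB019 and 8 to 7 on placebo (Section 9.2).

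**The stated follow-up.** Day 281 − Day 225 = 56 days = 8 weeks, which agrees with the protocol.

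**Completers, from the last dose.** 281 − 197 = 84 days = 3 × 28. With windows: (281 − 5) − (197 + 4) = 75 days to (281 + 5) − (197 − 4) = 93 days. The protocol does not state the 84 days; they follow from the schedule.

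**Withdrawn before dosing at a dosing visit.** The nominal gap is 28 days. The windows of the two visits widen it:

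- Day 29: 28 ± (0 + 2) = 26 to 30 days
- Day 57: 28 ± (2 + 4) = 22 to 34 days
- Day 85 onward: 28 ± (4 + 4) = 20 to 36 days

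**Share of the last dose left,** taken as 2^(−t/28):

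| Situation | Days since last dose | Share left |
|---|---|---|
| ET at Day 8 | 7 | 84% |
| ET predose, Day 29 | 28 (26 to 30) | 50% (53% to 48%) |
| ET predose, Day 57 | 28 (22 to 34) | 50% (58% to 43%) |
| ET predose, Day 85 onward | 28 (20 to 36) | 50% (61% to 41%) |
| 8 weeks after last dose | 56 | 25% |
| Completer at Day 281 | 84 (75 to 93) | 12.5% (16% to 10%) |

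This is simple decay of the last dose. It ignores subcutaneous absorption and earlier doses, and applies only to subjects who received ANB019. Counting earlier doses raises the amount: 400 mg on Day 1 decays to 200 mg by Day 29; adding 200 mg gives 400 mg, which is again 200 mg before the next dose. So a fully dosed subject leaving predose still has the equivalent of one 200-mg dose, against 400 × 0.125 = 50 mg for a completer at Day 281.

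**Days not covered at a 28-day ET.** 84 − 28 = 56 against the completers' schedule, or 56 − 28 = 28 if the stated 8 weeks is counted from the last dose.

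**Subjects affected, at planning.** 16 − 14 = 2 on ANB019 and 8 − 7 = 1 on placebo, so 3 of 24 (24 × 0.11 = 2.6) to Week 16. Removing consent withdrawal and loss to follow-up lowers this. Dropout in the extension is not stated.

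**The case against.** The strongest case concerns weight. The group is narrow: treatment-only and rescue-related discontinuers keep their follow-up, pregnancies are followed to outcome, and consent withdrawal and loss to follow-up cannot be remedied. The 84 days is not a protocol standard. It arises because the extension runs 28 days past its last dose, and completers also stop with some drug left. Section 8.2.1.4 requires proactive follow-up after an AE is reported, so a subject withdrawn for an event is likely to stay in contact. Section 10.1.2 provides for subjects to be contacted if the study is stopped. The AE row of Table 1 is marked as continuous. Finally, the trial was terminated and no subject reached the extension (SAP Sections 1 and 3.1), so nobody had the Day 197 to Day 281 interval.

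The narrow group and the derived status of the 84 days both stand, and they keep the point minor. The follow-up duty and the termination notice do not answer it: one follows a reported event and the other tells subjects about schedule changes, and neither collects new events. The continuous AE row does not override the end of collection in Section 8.2.1.4. Termination means that the change mainly serves later protocols that reuse this wording.

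**Conclusion.** The point holds as a minor, low-priority improvement. For subjects withdrawn from the study, active collection of new AEs and SAEs can end about 28 days after the last dose, with about half of it left, or sooner if they leave between visits. Completers have 84 days. This rests on the stated half-life, simple decay, and reading the end of participation for all AEs as the EOS/ET visit, which the text says outright only in the SAE sentence.

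A reader might infer more than the documents support:

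- **Everyone who stops treatment loses follow-up.** Sections 7.1 and 6.5.3 say otherwise.
- **The protocol caps follow-up at 28 days.** It sets no figure. The 28 days follows from the dosing interval, and an ET after missed doses or during the follow-up period would fall later.
- **SAEs after the ET visit go unreported.** Those the Investigator learns of and considers related must still be reported.
- **Safety data were lost in this trial.** The SAP does not say how many subjects were dosed or how long they were followed, so no actual loss can be shown.

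**What to change.** In Table 1, footnote b and Section 7.2, add that subjects withdrawn from the study, including by the Sponsor, who have not withdrawn consent or been lost to follow-up will be telephoned for new AEs and SAEs at 56 days (the stated 8 weeks) and 84 days (matching completers) after the last dose. Any call that would fall before the ET visit is skipped. If the sponsor prefers to keep to the stated 8 weeks, the 56-day call alone is the minimum. The choice between 56 and 84 days is a judgement.

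In Sections 8.2.1.4 and 6.7, end AE and SAE collection for these subjects at the later of the ET visit and the last such call, so that the release from seeking events applies only after that.

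Matching edits are needed in Section 8.2.8 and Table 1, footnote p, which list only the Day 3, 15, 43 and 71 calls. They are also needed in SAP Appendix 1, where the last-participation date and Last Study Day do not count a call after the ET visit. The TEAE definition in Section 9.4.8.1 has no upper time limit and can stay.

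The cost is these text edits, one or two calls per withdrawn subject by a method the protocol already uses, and a later last-contact date for a few subjects.

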2 INTRODUCTION

2.1 STUDY RATIONALE

The ichthyoses are a group of rare chronic genetic disorders that share characteristics of scaling and underlying skin inflammation to varying degrees. The occurrence of scaling is thought to be a compensatory cutaneous response to the inadequate, abnormally differentiated epidermal barrier. The quality of life of affected patients is poor, particularly owing to the highly visible and disfiguring skin alterations, the frequently associated severe pruritus, and the functional limitations related to thickened skin. Therapy for the ichthyoses has been limited to use of emollients and agents that peel the thick scales, specifically keratolytics and retinoids.

Among currently available treatments, oral retinoids appear to be the most effective, but they tend to increase ichthyosis-associated skin inflammation. Use of retinoids also is associated with potential side effects; they function by removing the compensatory scales without targeting the underlying disease process. Thus, there remains a huge unmet need for effective and safe treatments for these forms of ichthyosis, ideally therapy that both improves the scaling and decreases the cutaneous inflammation with its accompanying pruritus and discomfort.

Recent studies of the skin of patients with clinically confirmed diagnosis of a variety of types of ichthyosis showed a cutaneous biomarker pattern of the Th-17 pathway with the highest levels of expression of IL-36, specifically IL-36 β/γ (Paller 2017, Malik 2019, Czarnowicki 2018). Indeed, a sustained activation of the IL-36 pathway was observed in ichthyosis skin biopsies compared with normal and chronic plaque psoriasis skin biopsies, suggesting a key role of IL-36 inflammatory axis as a main driver of the disease. The increases in IL-36 cytokines, as well as their receptor (IL-36R) found in all forms of ichthyosis studied to date suggests that IL-36 β/γ could play an important role in amplifying the clinical manifestations of this debilitating skin disorder.

ANB019 is a high affinity, humanized immunoglobulin G4 (IgG4) monoclonal antibody (mAb) that specifically binds IL-36R and antagonizes IL-36 signaling. The IL-36 cytokines (IL-36 α , IL-36 β , and IL-36 γ) engage with IL-36R to initiate signaling events leading to proinflammatory responses. Interleukin 36 signaling is counter balanced by IL-36R antagonist (IL-36Ra), an IL-36 receptor antagonist that binds to IL-36R and competes with activity of IL-36 cytokines. Because IL-36 pathway has been implicated in amplifying inflammatory skin diseases, including ichthyosis, inhibition of IL-36 signaling, by targeting IL-36R with a specific mAb, may represent a novel strategy to control the pathological inflammatory cascade driven by IL-36 pathway activation. ANB019 is currently being studied as a potential first-in-class therapy for several cutaneous indications, including palmoplantar pustulosis (PPP), generalized pustular psoriasis (GPP), ichthyosis, and other inflammatory diseases where the IL-36 pathway may play a significant role in augmenting the disease. ANB019 may be beneficial in suppressing the inflammation, improving the pruritus, and possibly decreasing the scaling in patients with several types of ichthyosis.

This study is designed to evaluate the efficacy and safety of ANB019 in subjects with ichthyosis subtypes in which elevated expression of IL-36 has been confirmed (Paller 2017, Malik 2019, Czarnowicki 2018).

DocuSign Envelope ID: E4BE9C16-DB1E-4354-B874-2109B7254DAA

Efficacy and Safety of ANB019 in Subjects with Ichthyosis
Protocol ANB019-206

Version 1.0
30 October 2020

2.2 BACKGROUND

2.2.1 NONCLINICAL STUDIES

ANB019 exhibits strong inhibitory activity for human as well as cynomolgus monkey IL-36R (cyIL-36R) cell populations. Nonclinical data obtained from studies with ANB019 in primary human and cynomolgus monkey cells and from *in vivo* nonhuman primate studies demonstrated that:

- ANB019 shows reactivity with human and cynomolgus monkey IL-36R (dissociation constant [KD] of 67.9 ± 31.4 pM and 80.0 ± 49.6 pM, respectively), but not with mouse or rat IL-36R.
- In primary human and cynomolgus monkey cell populations, keratinocytes, peripheral blood mononuclear cells (PBMCs), and human whole blood, ANB019 inhibited IL-36R mediated release of IL-8.
- The terminal half-life ($t_{1/2}$) of ANB019 in cynomolgus monkeys was 304 hours after single intravenous (IV) dose administration, and 310 hours after a single SC dose administration at 10 mg/kg, with bioavailability approximately 76% consistent with the anticipated PK characteristics for a human IgG4 scaffold mAb in the cynomolgus monkey.
- Repeat-dose, Good Laboratory Practice (GLP) toxicity and toxicokinetic (TK) studies of 4, 13, and 26 weeks in duration have been conducted with ANB019 administered by weekly SC and IV injection in cynomolgus monkeys. There were only minor treatment-related injection site findings in the 4-week repeat-dose study. Treatment-related effects in the 13-week toxicity study included increased observations of nonformed feces and prolapsed rectum, and protozoa in the stomachs of cynomolgus monkeys; the latter being consistent with the mechanism of action of an immune-modulator in cynomolgus monkeys (Dubey 2002). Weekly administrations of vehicle control article, 30 mg/kg/dose ANB019 via SC injection, or 60 mg/kg/dose ANB019 via SC or IV bolus injection, to male and female sexually mature cynomolgus monkeys during the 26-week toxicity and TK study was well tolerated. ANB019-related effects were limited to a low incidence of liquid feces not considered AEs for animals administered 60 mg/kg/dose IV. Thus, the no observed adverse effect level (NOAEL) is 60 mg/kg/dose administered by SC or IV injection.

These data provide a strong scientific rationale for advancing ANB019 through clinical development.

A detailed description of the physical, chemical, and pharmaceutical properties of ANB019 and nonclinical studies is provided in the Investigator's Brochure (IB).

2.2.2 CLINICAL STUDIES

Currently, two clinical studies (ANB019-001 and ANB019-005) have been completed. Study ANB019-001 was a Phase 1, first-in-human, single ascending dose (SAD) and multiple ascending dose (MAD) study in healthy volunteers and in subjects with psoriasis. Study ANB019-005 was a Phase 1, ethno-bridging study, a single-dose safety, tolerability, PK, and immunogenicity study of ANB019 in healthy Japanese and Caucasian subjects. A detailed description of the safety and tolerability, and PK/pharmacodynamic (PD) results of these two Phase 1 clinical studies is provided in the IB.

In addition, two Phase 2a studies (ANB019-002 and ANB019-003) to evaluate clinical activity and safety of ANB019 in GPP and PPP are ongoing. Study ANB019-002 is a single-arm, multiple-dose study to be conducted in subjects with active GPP. Study ANB019-003 is a randomized, placebo-controlled, multiple-dose study to be conducted in subjects with PPP.

DocuSign Envelope ID: E4BE9C16-DB1E-4354-B874-2109B7254DAA

Efficacy and Safety of ANB019 in Subjects with Ichthyosis
Protocol ANB019-206

Version 1.0
30 October 2020

2.3 RISK/BENEFIT ASSESSMENT

2.3.1 KNOWN POTENTIAL RISKS

No major toxicities were observed in the 4-week repeat-dose toxicity study in cynomolgus monkeys. The main finding consisted of minor, injection site reactions associated with the SC route of administration and not considered AEs.

In cynomolgus monkeys, treatment-related effects observed in the 13-week repeat-dose toxicity study included protozoa in the stomach, an increase in nonformed feces and prolapsed rectum observations; the latter observation was not considered dose related. The increase in protozoa in the stomach has been observed in monkeys treated with immune-modulating drugs ([Dubey 2002](#)) and is consistent with the putative mechanism of action of ANB019. During the 26-week repeat-dose toxicity study, ANB019-related effects were limited to a low incidence of liquid feces. In the monkeys, the increased incidence of protozoa, nonformed feces, and prolapsed rectum were not considered AEs as they responded to veterinarian intervention. In humans, gastrointestinal infections can be clinically monitored and, in the case of most protozoa, are readily treatable even in the context of immunocompromised individuals ([Farthing 2006](#)).

One female monkey receiving 60 mg/kg ANB019 IV was found moribund on Study Day 34. The cause of death was not determined and had an uncertain relationship to ANB019 but could be due to treatment-related immune modulation. However, data published on IL-36R deficient humans shows no deleterious effect on general health, and normal immune function is broadly preserved, indicating that inhibition of IL-36R, does not generally compromise host defenses. Similar to other immune-modulating treatment paradigms, subjects should be closely monitored for any clinical gastrointestinal manifestations including infections and evaluated on an ongoing basis. If a gastrointestinal infection is suspected, the subject should be treated as clinically indicated.

